# 8.4 Analyses

# 8.4.1 Demographics and Baseline Characteristics

Baseline demographic characteristics (age, gender, race, ethnicity, weight) and other important baseline biomarkers and clinical measures (A $\beta$ 42, ADAS-cog, etc) will be summarized by randomized treatment group and overall for the Randomized Sample. The mean, median, range and standard deviation will be used to describe continuous variables. Frequency distributions will be tabulated for categorical variables.

#### 8.4.2 Safety Analyses

Safety and tolerability will be evaluated by reports of adverse events (AEs) and clinically significant changes in ECGs, Safety Head MRI findings, vital signs, physical examination

findings and laboratory tests. The incidence of adverse events will be tabulated by treatment, according to severity, and drug-relationship. All safety analyses will be performed on the safety sample; subjects will be analyzed as treated. Special safety lab results, such as notch lymphocyte, GI and renal safety test, will be included in laboratory analyses. Safety analyses will be performed separately for the double-blind phase and for the safety follow-up phase. The safety data presentation for the follow-up phase will be by the original assigned treatment.

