### Study Schematic

Due to the early termination of this study, the duration of study treatment and performance of the protocol specified termination procedures will not be completed according to the design of the

protocol as previously described. All subjects still receiving study medication at the time of study termination by sponsor will be contacted by the site promptly, instructed to stop dosing, and will be asked to return for an End of Treatment a (EOT) Visit. When the data for that EOT visit has been entered into the EDC system, the treatment code will be provided to the study site. Subjects treated with avagacestat will be scheduled for the Post Treatment/Study Termination Safety Follow-up Visits (to occur 4 Weeks, 12 Weeks, and 24 Weeks after last dose). Subjects who were randomized to the placebo arm, and those enrolled in the observational cohort will be advised of their treatment group and told that no further assessments are required.

Avagacestat-treated subjects should be scheduled for a 4 Week, 12 Week, and 24 Week Post Treatment Safety Follow-up Visit as outlined in Table 6.1-4. All attempts should be made to complete the three Post Treatment/Study Termination Safety Follow-up Visits.

Avagacestat treated subjects participating in the long-term safety follow-up phase **for 12 weeks or less** should be scheduled for a 12 Week Post Treatment/Study Termination Safety Follow-up Visit, as well as for a 24 Week Post Treatment/Study Termination Safety Follow-up Visit for a comprehensive skin examination by a dermatologist (or dermatologic physician's assistant in the United States);

Avagacestat-treated subjects participating in the long-term safety follow-up phase **for greater than 12 weeks** should only be scheduled to return for the 24 Week Post Treatment/Study Termination Safety Follow-up Visit for a comprehensive skin examination by a dermatologist (or dermatologic physician's assistant in the United States).

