Additionally all subjects who previously discontinued from this study (ie, those who did not participate in the long-term follow-up) but were exposed to greater than one month (31 days) of treatment with avagacestat should be contacted by the site and scheduled to complete the 24 Week Post Treatment/Study Termination Follow-up Visit for a comprehensive skin examination by a dermatologist (or dermatologic physician's assistant in the United States), irrespective of whether they received. a comprehensive skin examination with a dermatologist (or dermatologic physician's assistant in the United States) at the end of study treatment.

The study is a multi-center, randomized, double-blind, 2-arm, placebo-controlled, parallel-group study in patients with prodromal Alzheimer's disease to evaluate safety, tolerability, pharmacodynamic and pharmacokinetic effects of once-daily dosing of BMS-708163 for a minimum of 104 weeks (refer to Study Schematic in Figure 4.1-1 above).

The treatment period for the study will be a minimum of 104 weeks (2 years). Randomized subjects may continue in the study beyond 104 weeks of treatment (up to an estimated maximum of 220 weeks of treatment) until the last randomized subject has had the opportunity to receive study medication for approximately 104 weeks. Thus, given the recruitment period of approximately 27 months, the overall duration of study treatment is expected to last between 104 and 220 weeks for a given subject. The study treatment phase will end once the last randomized subject has completed approximately 104 weeks of treatment (estimated to occur by September, 2013). All subjects still receiving study medication at the time last patient last

Revised Protocol No.: 10

treatment is determined will end treatment and be followed in the Safety Follow-up Visits (4 Weeks and 12 Weeks post end of treatment visit; refer to Section 6.1.1.7).

After assessments of eligibility during the maximum 75 day screening period, subjects will undergo baseline safety and PD assessments. In a subset of subjects, at selected centers, subjects may be consented for 24-hour intensive PK assessments. In another subset of sites, subjects may be consented for PET imaging assessments at pre-specified visits (delineated in a separate, site-specific amendment).

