#### 8 STATISTICAL CONSIDERATIONS

# 8.1 Sample Size Determination

The primary endpoint of this study is safety and tolerability. The sample size of 135 subjects per group is chosen empirically rather than based on the statistical power consideration. However, it should be noted that with 135 subjects per dose group, the probability of observing at least one specific AE is satisfactorily high at each dose group if the true event rate of that AE is within the commonly observed ranges, as shown in Table 8.1-1 with a list of assumed true event rates. For example, the probability of observing at least 1 specific AE is 98% at each dose group if the true event rate of that AE is 3% (Table 8.1-1). Table 8.1-2 shows the probability of observing at least one event difference assuming different event rates for each treatment group. In addition, the 95% exact confidence interval of 10% (13 events out of 135 subjects) event rate in each group is (0.05, 0.16).

Table 8.1-1: Probability of Observing a Given Adverse Event

Assumed AE incidence rate	Probability of observing at least 1 AE out of 135 patients a
0.1%	12.6%
0.5%	49.1%
1%	74.2%
2%	93.5%
3%	98.4%

Assumes a distribution of Binomial (n = 135, probability of event given in the first column).

Table 8.1-2: Probability of Observing at Least One Incidence Difference

AE incidence rate (%) for Placebo		AE incidence rate (%) for Active						
		0.1	0.5	1	2	3		
	0.1	22.3%						
	0.5	51.4%	60.9%					
	1	73.2%	71.8%	74.1%				
	2	92.0%	87.0%	83.2%	82.2%			
	3	97.6%	95.0%	90.9%	86.1%	85.6%		

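### Follow-up safety data are to be shown by assigned arm, but post-termination visits and recall skin examinations are done only in avagacestat subjects

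*Protocol*

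**What the plan says.** Protocol section 8.4.2 splits the safety analysis in two: "Safety analyses will be performed separately for the double-blind phase and for the safety follow-up phase". For the second part it adds: "The safety data presentation for the follow-up phase will be by the original assigned treatment". It draws no line between follow-up before the study was terminated and follow-up after it. All safety analyses are to use the Safety Sample.

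Section 4.1 (Study Schematic) describes what happens at termination. Subjects still on drug stop and attend an End of Treatment (EOT) visit, and the site receives the treatment code once that visit's data are entered. Avagacestat subjects then return at 4, 12 and 24 weeks. Placebo subjects "will be advised of their treatment group and told that no further assessments are required". Avagacestat subjects already in long-term follow-up come back for the 24-week skin examination, and those with 12 weeks or less of it also have the 12-week visit. Earlier dropouts who are not in long-term follow-up are recalled for that examination if they had more than 31 days on avagacestat, whether or not a dermatologist had already examined them at the end of treatment.

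**The concern.** Under the planned end of study, which section 4.1 still describes, everyone on drug at the last treatment date would have had the 4- and 12-week safety visits. A by-arm follow-up table fitted that design. It does not fit the terminated study, in which one arm is called back and the other is released. Section 8.4.2 was not brought into line.

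Long-term safety is the primary objective (section 2.1), and skin findings are clearly of interest, since a dedicated dermatology visit was added for them. In a table with an avagacestat column and a placebo column, a low placebo count would partly mean that nobody looked. The post-termination findings are also gathered with treatment known, which can affect what is reported and how it is attributed to drug.

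**Working it through.** **1. Who is observed, by window**

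| Window | Avagacestat | Placebo | Treatment known to site? | Protocol source |
|---|---|---|---|---|
| First dose to EOT visit, including the end-of-study dermatology examination | Yes | Yes | No | 4.1; Table 6.1-2 |
| Follow-up after stopping drug, before termination (+4/+12 weeks; 12-weekly long-term follow-up) | Yes | Yes | No unblinding described | 4.2.3; Tables 6.1-2, 6.1-4 |
| 4 and 12 weeks after termination (adverse events, laboratory tests, vital signs; structured skin examination at 12 weeks) | Yes | None for subjects on drug at termination | Yes | 4.1; Table 6.1-4 |
| 24 weeks (dermatology skin examination only), including recalled dropouts | Yes | None | Yes, because selection is by treatment | 4.1; Table 6.1-4 |

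The first two rows are the same for both arms. The last two are avagacestat-only. Section 8.4.2 puts rows two to four under one heading, the follow-up phase, and splits it by arm.

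**2. Denominators.** If the denominator is the Safety Sample, placebo subjects who were never examined count as event-free. If it is subjects with a follow-up visit, the placebo column holds only people who stopped drug before termination, while the avagacestat column also holds people who stayed on drug until termination. Neither gives a like-for-like comparison.

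**3. The plan's own figures.** Section 8.1 uses 135 per arm. Table 8.1-1 for a 3% event rate: 1 − (1 − 0.03)^135 = 98.4%, as stated. The exact 95% interval for 13/135 is 0.052 to 0.159, which agrees with the stated 0.05 to 0.16. These figures are sound, but they assume that all 135 subjects are observed. With n = 0 observed, 1 − (1 − p)^0 = 0 for any event rate p. That is the position of placebo subjects on drug at termination, once the EOT visit is past.

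**4. Illustration of size.** The documents give neither event rates after treatment nor the number of avagacestat subjects seen after termination. Assume the same constant hazard r in both arms (true ratio 1) and N avagacestat subjects examined, with N from 50 up to the planned 135.

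Expected subjects with an event over 24 weeks: N × [1 − exp(−r × 24/52)].

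| r per year | N = 135 | Chance of at least one | N = 50 | Chance of at least one | Placebo, on drug at termination |
|---|---|---|---|---|---|
| 0.01 | 0.62 | 0.46 | 0.23 | 0.21 | 0 |
| 0.05 | 3.08 | 0.96 | 1.14 | 0.69 | 0 |
| 0.10 | 6.09 | 0.998 | 2.26 | 0.90 | 0 |

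The 24-week window applies to skin findings only. Other adverse events are collected to 12 weeks. With 12/52 in the formula, r = 0.01 gives 135 × 0.0023 = 0.31 and r = 0.10 gives 135 × 0.0228 = 3.08.

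**The case against.** The strongest reply is that the protocol already keeps the two phases apart, so avagacestat-only visits never enter the double-blind tables, where the main randomised safety comparison sits. That is correct, and it limits this point to the follow-up display.

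The display is also only a presentation; section 8.4.2 plans no test or ratio on it. That lowers the stakes, but two columns side by side invite comparison all the same.

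Nor is placebo follow-up empty. Section 4.2.3 sends everyone who stops drug into follow-up (withdrawal of consent and loss of ability to consent freely aside). The follow-up columns of Table 6.1-2 and the long-term follow-up column of Table 6.1-4 carry no arm restriction, and the end-of-study dermatology examination is for both arms. All this stands: the gap concerns what is found after termination. It does not rescue a pooled table, because the placebo data come from a different set of visits.

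A reader might infer something stronger: that the arms are not comparable for safety at all, because adverse events are summarised as simple percentages ("The incidence of adverse events will be tabulated by treatment, according to severity, and drug-relationship") while exposure is unequal. The documents do not support that. Section 4.1 says that "the overall duration of study treatment is expected to last between 104 and 220 weeks for a given subject", but this spread follows from entry date and a common calendar stop, which randomisation balances in expectation. No section reports exposure or discontinuation by arm. At an assumed 0.10 events per year in both arms, exposures of 2.0 years (placebo) and 1.5 years (avagacestat) would give 18.1% and 13.9%, a ratio of 0.77. Equal exposure gives 1.00, and nothing in the protocol favours the first case. Exposure-adjusted rates may also be in the SAP, which was not at hand, so their absence from the protocol is not an error.

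**Conclusion.** The point holds for the follow-up phase only. The by-arm rule in section 8.4.2 conflicts with the avagacestat-only, unblinded post-termination follow-up in section 4.1. Run as written, it would show late skin and other events under avagacestat with no placebo observation to set against them.

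The asymmetry follows from the protocol text and needs no assumption. Its size does: the range of 0.2 to 6.1 expected avagacestat events over 24 weeks rests on assumed hazards of 0.01 to 0.10 per year and 50 to 135 subjects examined. The zero applies to placebo subjects still on drug at termination and to the 24-week examination, not to placebo follow-up as a whole. The double-blind comparison is not called into question.

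**What to change.** Amend section 8.4.2, and carry the change into the SAP, as follows:

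- Summarise post-termination data, including the 24-week and recall skin examinations, for avagacestat only. Label them descriptive, uncontrolled and unblinded. Use the number examined as denominator and give time since last dose.
- Show pre-termination follow-up in a separate table.
- Limit between-arm safety comparisons to windows observed in both arms: first dose through the EOT visit, with pre-termination follow-up shown on its own.
- While the section is open, reconcile its as-treated rule for all safety analyses with assigned treatment for follow-up. The two differ for any subject who received the wrong treatment.

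Optional, and not the correction of an error: because individual exposure varies and was cut short by termination, show exposure-adjusted adverse event rates beside the percentages, in case discontinuation turns out to differ by arm. Such rates assume a roughly constant hazard.

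The cost is a few sentences and some extra tables. No visit, assessment or clinical rule changes. What is given up is a single combined follow-up table.

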# 8.4.3 Efficacy Analyses

Confidence intervals will be reported at the 95% level, if not otherwise specified.

In order to assess the predictive value of baseline CSF biomarkers (A $\beta$ 40, and A $\beta$ 42, total Tau, total Tau/A $\beta$ 42 ratio, and phosphorylated Tau) on progression to dementia, the relationship between each of CSF biomarker and time to progression to dementia will be assessed by separate stratified Cox proportional hazards model on the Randomized Sample. The Cox model will include treatment, age, gender, education and individual baseline biomarker as covariates and ApoE4 status and baseline status of acetylcholinesterase inhibitor treatment as stratified variables. The parameter estimate and 95% CI for the hazard ratio for one unit increase in the biomarker will be reported. Patients who do not have progression to AD will be censored on their last visit date.

In order to validate  $A\beta42$  screening cutoff point of 200 pg/mL, stratified logistic analysis will be carried out on the combined dataset of placebo group and observational cohort. The logistic model will have progression to AD (yes/no) as a binary dependent variable and age, gender, education and  $A\beta42$  screening value as covariates and ApoE4 status and baseline status of acetylcholinesterase inhibitor treatment as stratified variables.

Time to progression to dementia will be obtained from Kaplan-Meier maximum likelihood estimates for each treatment group on the Randomized Sample.

For each of the continuous efficacy outcome measurements (CDR-SB and ADAS-Cog, etc), the change from baseline to post-baseline scores (up to 24 months) over time from the Randomized Sample will be analyzed using a linear mixed effects model repeated measures (MMRM) with maximum likelihood estimation. The model will include treatment, time, baseline primary efficacy score, the interaction between baseline primary efficacy score and time, baseline MRI volume, APOE status, baseline status of acetylcholinesterase inhibitor treatment and the interaction between treatment and time as covariates. Time is classified into months (3, 6, 9, 12, 15, 18, 21, and 24) and treated as a categorical variable. An unstructured covariance matrix will be used to represent the correlation of the repeated measures within each subject. Model based adjusted mean change score from baseline (LS means) at each study month and 95% CI for the treatment difference will be reported.

Pearson's correlation coefficient will be used to estimate the linear relationship between clinical outcomes such as CDR-SB with biomarkers at study months when both measurements are available. Post-treatment follow-up data from the safety follow-up phase will be considered in sensitivity analyses. Trending of clinical rating scales during the active treatment period differing

from those after discontinuation from treatment will be investigated. Number of progressions after study medication discontinuation will also be tabulated, but will not be adjudicated.

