# 2.2 Secondary Objectives

To assess the predictive value of CSF biomarkers (A $\beta$ 40, and A $\beta$ 42, total Tau, total Tau/A $\beta$ 42 ratio, and phosphorylated Tau) on progression to dementia.

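### The Cox models for the CSF biomarkers cannot separate a marker's own predictive value from baseline severity, and a hazard ratio per raw unit does not measure predictive performance

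*Protocol*

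**What the plan says.** Protocol 2.2 gives the trial one secondary objective: "To assess the predictive value of CSF biomarkers" (Aβ40, Aβ42, total tau, the total tau/Aβ42 ratio and phosphorylated tau) for progression to dementia. It does not say whether this means value in itself or value beyond the clinical picture.

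Protocol 8.4.3 fixes the analysis as a separate Cox model for each marker on the Randomized Sample:

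- Covariates: "The Cox model will include treatment, age, gender, education and individual baseline biomarker as covariates".
- Strata: "ApoE4 status and baseline status of acetylcholinesterase inhibitor treatment as stratified variables".
- Output: "The parameter estimate and 95% CI for the hazard ratio for one unit increase in the biomarker will be reported".

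No cognitive or functional score is on the list. Table 6.1-1 schedules both CDR-SB and ADAS-cog at Screening and Baseline. Section 8.4.1 counts ADAS-cog among the "other important baseline biomarkers and clinical measures" to be summarised, which shows that the score will be at hand but not that it enters the model. No rule says when a marker counts as predictive.

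**The concern.** Within prodromal AD, subjects differ in how close they already are to dementia. A CSF marker may be associated with time to dementia because it carries information of its own, or because it runs in parallel with present impairment. The planned models already condition on age, gender, education, ApoE4 and ChEI use, so they are not a purely marginal look at the marker. They omit the clinical variable most directly tied to the outcome. Their hazard ratio is then neither the marker's unadjusted predictive value nor its value beyond what a clinician already knows.

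The form of the output is a separate matter. A hazard ratio measures association, and a clearly non-null one can go with weak discrimination between progressors and non-progressors. One unit of Aβ42 is 1 pg/mL, while one unit of the tau/Aβ42 ratio is a large step on a scale whose entry cut-off is 0.39. The five hazard ratios cannot be read against each other.

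At stake is the interpretation of the only secondary objective. The primary objective is safety and is not affected.

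**Working it through.** **The plan's own figures.** The protocol gives no power or event count for the Cox models: "The sample size of 135 subjects per group is chosen empirically rather than based on the statistical power consideration". Its sample-size figures concern adverse events, and they reproduce. For example, at a 3% rate, 1 − 0.97^135 = 98.4%, as in Table 8.1-1.

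**Inputs from the protocol.** 2 × 135 = 270 randomized (8.1); progression of 25% per year (4.4), so the yearly hazard is −ln(0.75) = 0.288; planned treatment of 104 to 220 weeks (4.1); Cox covariates and four strata (8.4.3).

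**Assumed, because the protocol does not give them.** Correlation ρ between marker and baseline severity of 0 to 0.5; severity hazard ratio of 1.5 or 2.0 per SD; dropout of 15% per year.

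**Model.** Severity S is standard normal. The marker is M = ρS + √(1 − ρ²)·ε. The event hazard is 0.288·exp(ln(HR_S)·S), so M has no effect of its own. The protocol's stratified Cox model was fitted with and without S, 500 runs per setting, about 130 events per run. Simulation error near 5% is about ±2 points.

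| ρ | HR_S | Marker HR per SD, protocol model | CI excludes 1 | Marker HR, S added | CI excludes 1 |
|---|---|---|---|---|---|
| 0 | 1.5 / 2.0 | 1.00 / 1.00 | 5% / 6% | 1.00 / 1.00 | 4% / 7% |
| 0.1 | 1.5 / 2.0 | 1.03 / 1.06 | 6% / 10% | 0.99 / 1.00 | 4% / 5% |
| 0.2 | 1.5 / 2.0 | 1.09 / 1.13 | 16% / 25% | 1.00 / 1.00 | 6% / 4% |
| 0.3 | 1.5 / 2.0 | 1.12 / 1.21 | 26% / 55% | 0.99 / 1.00 | 7% / 7% |
| 0.5 | 1.5 / 2.0 | 1.22 / 1.37 | 57% / 92% | 1.00 / 1.00 | 5% / 6% |

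**Check by hand.** Without S, the marker's log hazard ratio is about ρ·ln(HR_S). At ρ = 0.3 and HR_S = 1.5 this is 0.3 × 0.405 = 0.122, a hazard ratio of 1.13 (simulated 1.12). The share of CIs excluding 1 is about Φ(√130 × ln 1.12 − 1.96) = Φ(1.29 − 1.96) = 25% (simulated 26%).

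**Fewer events.** If early termination halved the events to 65 (an assumption), the same formula at ρ = 0.3 gives Φ(8.06 × 0.113 − 1.96) = 15% for HR_S = 1.5, and Φ(8.06 × 0.191 − 1.96) = 34% for HR_S = 2.0. The share falls, but the expected shift in the hazard ratio does not.

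**Price of adjusting.** A marker with a true own effect of 1.3 per SD, at ρ = 0.3, keeps 78-79% power with S in the model, and its estimate is 1.31. Without S the estimate is 1.45-1.52, because it also carries severity.

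**Hazard ratio against discrimination.** With a normal linear predictor of SD s = ln(HR), C = E[1/(1 + e^(−|D|))], where D ~ N(0, 2s²). For a hazard ratio of 1.3 per SD, s = 0.262 and C = 0.57. Power with 130 events is Φ(11.40 × 0.262 − 1.96) = Φ(1.03) = 85%. A marker can be very likely to show a CI clear of 1 and still discriminate poorly.

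**Effect of the unit.** The same 1.3 per SD reads exp(0.262/50) = 1.005 per pg/mL if the SD is 50 pg/mL, and exp(0.262/0.3) = 2.4 per unit of a ratio if the SD is 0.3. Both SDs are assumed.

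**The case against.** The strongest reply is that the objective asks for predictive value, not incremental or independent value. A marker that tracks how advanced a subject is does predict progression. Severity may also lie on the path from amyloid and tau pathology to dementia, so adjusting for it answers a different question. This stands. It is why the severity-adjusted model belongs beside the present one and not in its place, and why confounded is the wrong word.

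A reader might infer that a marker with nothing to add will be declared predictive. The documents do not support that. Section 8.4.3 promises an estimate and an interval ("Confidence intervals will be reported at the 95% level, if not otherwise specified") and states no decision rule. The percentages above count intervals that exclude 1 and nothing more. They also rest on an unknown correlation. The entry limits (CDR global 0.5, MMSE 24-30) narrow severity, and the CSF entry criteria narrow Aβ42 and the ratio. Both may lower the correlation, and at 0.1 the excess is small.

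A reader might also infer that the protocol contradicts itself, because its MMRM includes "baseline primary efficacy score, the interaction between baseline primary efficacy score and time, baseline MRI volume". That comparison is weak. The MMRM analyses change, and adjusting change for the same scale's starting value is routine. Time to dementia has no baseline value of its own.

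Nor does the plan contain nothing else on prediction. Section 8.4.3 adds a logistic model of progression on screening Aβ42 in the placebo group plus the observational cohort, and correlations of clinical scores with biomarkers. Neither measures discrimination, and the logistic model also omits severity.

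Finally, performance measures and supplementary models are often left to the SAP, which is not at hand and may add them. But 8.4.3 itself specifies covariates, strata and reported statistic without deferring to the SAP, so what it fixes can be judged.

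**Conclusion.** The point holds in a limited form. As specified, the five Cox models cannot tell a marker's own predictive value from baseline severity, and a hazard ratio per raw unit neither measures predictive performance nor allows comparison between markers. The second part needs no assumption about correlation.

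The size of the first part is conditional. With about 130 events and severity hazard ratios of 1.5-2.0 per SD, a marker that only tracks severity yields a CI excluding 1 in 6-10% of trials at correlation 0.1, rising to 57-92% at 0.5, against 4-7% with severity in the model. The documents give neither the correlation nor the severity effect. The entry limits may put the truth towards the low end, and early termination may reduce the events and with them these shares. This is a worthwhile, inexpensive improvement to a secondary analysis, not an error that invalidates it.

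**What to change.** In 8.4.3, keep the present Cox model and add for each of the five markers a second one that also includes baseline CDR-SB (or ADAS-cog), with one score chosen in advance for all markers. Report the hazard ratio per SD in both. Beside it, give Harrell's C, or the time-dependent AUC at 104 weeks, for the model with and without the marker. Because the models are stratified, C should compare subjects within strata. State in one sentence that the present model describes association without regard to baseline severity, and that the added one describes value beyond it.

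The cost is a few lines of text and code on data already scheduled, with no new assessment. The downside is slightly more analysis, and adjusted hazard ratios that may look less favourable to the markers.

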Free & Cued Selective Recall Reminding test		X	6.4.3.8
Montreal Cognitive Assessment (MoCA)		X	6.4.3.3
Sheehan Suicidality Tracking Scale (STS)	X	X	6.3.8.1
Columbia-Suicide Severity Rating Scale (C-SSRS)		X	6.3.8.2
Safety and Volumetric Head MRI	X	$X^b$	6.4.4.5
Concomitant Medication Tracking	X	X	5.5

All Screening assessments must be completed and the subject must meet all inclusion/exclusion criteria (with the exception of the  $A\beta42$  level of < 200 pg/mL or a Total Tau/A $\beta42$  ratio of  $\geq 0.39$ ) to be eligible for the Observational Cohort. Refer to Section 6.4.4.8 for additional details.

77

b On-study MRI should be done at the week 60 visit, or the next scheduled visit for subjects who have surpassed week 60.

<sup>c Only CNS acting medications are required to be captured for Observational Cohort participants.

Flow Chart for Protocol CN156018 - Long-Term Follow-up and Post Treatment/Study Termination Safety Follow-Up Visits Table 6.1-4:

Procedure	LTFU Every 12 Weeks (+ 7 days)	4 Week Post Txt	12 Week Post Txt	24 Week Post Txt a	Protocol Section
Assessments					
Assessment of Progression to Dementia	X		X		6.4.2.1
CDR-SB	X		X		6.4.2.2
MMSE	X		X		6.4.3.1
ADAS-COG	X		X		6.4.3.6
Geriatric Depression Scale	X		X		6.4.3.5
DSM-IV-TR	X		X		6.4.2.1
NINCDS-ADRDA	X		X		6.4.2.1
ADCS-MCI-ADL	X		X		6.4.3.10
Vital Signs	X	X	X		6.3.5
Physical Measurements	X	X	X		6.3.5
Routine Safety Laboratory Tests, including exploratory renal laboratory tests (central laboratory)	×	X	X		6.3.6.2
Renal (Cystatin C and Urine Microalbumin)			X		6.4.4.2
Comprehensive Structured Skin Examination			X		6.3.4
Comprehensive Skin Examination				X	6.3.4
12 Lead ECG (central laboratory)	X				6.3.1
Adverse Event Assessments	X	X	X		7.1
Concomitant Medication Tracking	X	X	X		5.5

a Post Treatment/Study Termination Safety Follow-up Visit at 24 Weeks will only include a comprehensive skin examination by a dermatologist (or dermatologic physician's assistant in the United States).

b Vital Signs include sitting and standing orthostatic pulse and blood pressure measurements.

c Weight measurements are to be completed during Long-term Follow-up.

d Only CNS acting medications are required to be captured for Long-term Follow-up participants.

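### The censoring date for time to progression is not tied to a dementia assessment, and skin-only visits that exist only for avagacestat subjects could lengthen that arm's event-free time

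*Protocol*

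**What the plan says.** The only censoring rule for progression closes the Section 8.4.3 paragraph on the Cox models for CSF biomarkers: "Patients who do not have progression to AD will be censored on their last visit date". Treatment is a covariate in those models. The comparison by arm follows two paragraphs later, with no censoring rule of its own: "Time to progression to dementia will be obtained from Kaplan-Meier maximum likelihood estimates for each treatment group on the Randomized Sample".

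Section 4.1 sets the visits after termination:

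- Active arm: "Subjects treated with avagacestat will be scheduled for the Post Treatment/Study Termination Safety Follow-up Visits (to occur 4 Weeks, 12 Weeks, and 24 Weeks" after the last dose.
- Placebo subjects and the observational cohort: they "will be advised of their treatment group and told that no further assessments are required".
- Earlier discontinuers who were not in long-term follow-up and who "were exposed to greater than one month (31 days) of treatment with avagacestat should be contacted by the site" are recalled for the 24-week visit, again for a skin examination.

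Table 6.1-4 marks the Assessment of Progression to Dementia at the 12-week visit and every 12 weeks in long-term follow-up, but not at the 4-week or 24-week visit. Its footnote a says: "Visit at 24 Weeks will only include a comprehensive skin examination by a dermatologist".

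Two other statements bear on the point. The last paragraph of Section 8.4.3 assigns data from the safety follow-up phase to sensitivity analyses, and says that progressions after stopping study drug will be counted but not adjudicated. Section 4.4 sends progressions up to and including the 12-week post-treatment visit to the Adjudication Committee.

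**The concern.** A subject can be counted as event-free only for as long as someone was looking for the event. A rule that censors at any last visit breaks this link when the last visit cannot detect progression. Here such visits are unequal by design: after termination, only avagacestat subjects have them. The added time enters that arm's risk sets with no chance of an event, so its apparent progression rate falls.

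If the rule is followed literally, the Kaplan-Meier curve for avagacestat sits too high and the treatment coefficient in each Cox model shifts in the drug's favour. Drug effect on progression is exploratory in Section 2.3, but Section 4.4 calls time to progression an important secondary outcome measure, so these curves are likely to be read.

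**Working it through.** **The plan's own figures.** The protocol gives no event count, hazard ratio or power for time to progression, so there is no figure on this point to reproduce. Its design probabilities concern adverse events. They are sound (for a 3% rate, 1 − 0.97^135 = 98.4%, as in Table 8.1-1) but have no bearing here.

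**Inputs from the protocol.** Progression of 25% per year (Section 4.4), so hazard = −ln(0.75) = 0.288 per year. 135 subjects per arm (Section 8.1). Recruitment of about 27 months = 117 weeks (Section 4.1).

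**Assumptions, not in the protocol.** Termination 143 to 195 weeks after first randomization. Discontinuation of 10% to 30% per year, equal in both arms. Recall visit 24 weeks after termination. All avagacestat discontinuers with more than 31 days of exposure eligible for recall.

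**Step 1: what one visit hides.** A non-progressor on avagacestat at termination is assessed at end of treatment and at 12 weeks, then seen at 24 weeks for skin only. That is 12 unassessed weeks, in which 1 − exp(−0.288 × 12/52) = 6.4% would be expected to progress unrecorded. Suppose, for illustration, that a subject stopped 52 weeks before termination and is recalled 24 weeks after it. The gap is 76 weeks, and the share is 1 − exp(−0.288 × 76/52) = 34%. The recall visits therefore matter most.

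**Step 2: effect on the hazard ratio.** Simulation with a true hazard ratio of 1, exponential progression, uniform accrual and a Cox model with treatment only; 800 trials for each combination of termination date and discontinuation rate. Ranges run over those combinations.

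| Reading of the rule | Unassessed share of avagacestat person-time | Average HR | Rejections favouring drug (nominal one-sided 2.5%) |
|---|---|---|---|
| Follow-up ends with treatment, both arms | 0 | 0.99–1.01 | 2–3% |
| Last dementia assessment, including the 12-week visit for avagacestat | 0 | 0.99–1.01 | 2–4% |
| 12-week visit assessed, censored at the 24-week visit | 3–8% | 0.93–0.98 | 3–6% |
| Progressions after stopping drug not counted, time run to 24 weeks | 7–18% | 0.86–0.95 | 4–9% |
| 24-week and recall visits, 50% attendance | 10–27% | 0.78–0.93 | 6–22% |
| 24-week and recall visits, full attendance | 18–42% | 0.67–0.87 | 10–49% |

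In the 50% row, attendance applies to all post-treatment visits, not only to the recall visit.

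**Step 3: plausibility.** If a share u of person-time is unassessed, the crude rate falls by the factor 1 − u. For the 24-week visit alone this gives 1 − 0.08 = 0.92 to 1 − 0.03 = 0.97. For 50% attendance it gives 1 − 0.27 = 0.73 to 1 − 0.10 = 0.90. The Cox figures are somewhat milder, as expected: added time counts only where events still occur in the risk set, and much of it falls late.

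**The case against.** The strongest reply is that Section 8.4.3 itself assigns safety follow-up data to sensitivity analyses. On that reading the main analysis ends with treatment, the hazard ratio is about 1.0, and nothing is biased. This stands as a possible reading, so a reader who infers that the analysis is certainly biased goes too far. It does not settle the matter. The sentence limits the use of follow-up data, not the censoring date, and Section 4.4 points the other way by adjudicating progressions up to the 12-week visit.

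Other limits also stand:

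- The rule is written for the biomarker models, where the reported hazard ratio is the biomarker's. Treatment is randomized and should be roughly unrelated to baseline biomarkers, so no distortion of that estimate is shown.
- Section 8.4.3 states no log-rank test or treatment hazard ratio. The rejection rates above gauge the size of the shift. They are not the error rate of a planned test.
- Not all post-termination time is unassessed. The 12-week and long-term follow-up visits assess progression, although at the 12-week visit the site may already hold the treatment code.
- The recall rows treat every earlier discontinuer as outside long-term follow-up. Those inside it were assessed every 12 weeks, so their gaps are shorter.
- Table 6.1-2 has +4 and +12 week safety visits that are not restricted by arm and, as far as the table can be read, have no progression assessment. A literal rule would lengthen some placebo follow-up too; the simulation leaves this out.

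A reader might also infer that unequal follow-up by arm is dependent censoring in itself. It is not: Kaplan-Meier by arm, and Cox with treatment in the model, both allow censoring to differ between arms. The second row of the table shows this, since an assessed 12-week visit in one arm only leaves the hazard ratio at 0.99 to 1.01. The fault is time without ascertainment.

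Finally, the SAP may define the date more closely. But the protocol does state a rule, and that rule does not fit its own visit schedule.

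**Conclusion.** The point holds as a badly fixed rule whose literal reading favours avagacestat. The direction follows from the visit schedule. The size depends on which visits count: about 0.93 to 0.98 from the 24-week visit alone, and about 0.78 to 0.93 once recall visits are added at 50% attendance, against a true value of 1. These figures rest on assumed termination dates, discontinuation rates, recall timing and attendance, none of which the protocol gives. If follow-up data stay out of the main analysis there is no such bias, but the protocol does not say so clearly. Sections 4.4 and 8.4.3 also disagree on whether progressions after stopping drug are adjudicated, which leaves the end of follow-up uncertain. Severity is moderate: the primary objective is safety, the drug effect on progression is exploratory, and the sample size is not based on power.

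**What to change.** Replace the censoring sentence in Section 8.4.3 with one to this effect: subjects without progression are censored at the date of their last completed Assessment of Progression to Dementia, under the same rule in both arms and in both the Kaplan-Meier and Cox analyses; visits without that assessment never extend follow-up. Name those visits: the 4-week, 24-week and recall skin visits, and the +4 and +12 week safety visits of Table 6.1-2.

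Then state whether the assessed 12-week post-treatment and long-term follow-up data enter the main analysis or only the sensitivity analysis, and reconcile Sections 4.4 and 8.4.3 on adjudication of progressions after study drug is stopped. A cut-off at the end-of-treatment visit is one possible choice, but it is not needed to remove this bias and would set aside assessed data.

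The cost is a few sentences and a change to one derived date. No new data are needed.
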